6.3.4 Simpson Angus Scale

The Simpson Angus Scale (SAS) ([Simpson and Angus 1970](#)) is composed of 10 items and is used to assess pseudoparkinsonism. The grade of severity of each item is rated using a 5-point scale. Total SAS scores can range from 0-40. Signs assessed include gait, arm-dropping, shoulder shaking, elbow rigidity, wrist rigidity, leg pendulousness, head dropping, glabella tap, tremor, and salivation. In more than 1 randomized controlled trial of bipolar I disorder ([Tohen et al., 2004](#)), treatment-emergent parkinsonism was defined as a SAS score of greater than 3 at any time following a score of 3 or less.

6.3.5 Demographics, Medical History, and Medication History

A complete medical and psychiatric history will be obtained from each potential subject at the visits indicated in [Table 2](#). Demographic information, including date of birth, gender, race, and ethnicity will be recorded as well. Any new medical condition reported after the informed consent form (ICF) has been signed will be captured as an AE. In addition, a history of the medications that the subject has taken for the current depressive episode should be obtained. Subjects may be asked to provide pharmacy or medical records to substantiate the medication history.

6.3.6 Physical Examinations

A general physical examination will be conducted at the visits indicated in [Table 2](#).

6.3.7 Vital Signs

Vital signs will be collected at the visits indicated in [Table 2](#).

Vital signs will include resting respiration rate, sitting systolic and diastolic blood pressure (BP), pulse rate, and temperature. The sitting BP should be measured after the subject has been sitting for ≥ 3 minutes.

6.3.8 Height, Weight and Body Mass Index

Height (in cm) will be measured at the Screening visit only.

Body weight (in kg) will be measured at the visits indicated in [Table 2](#).

Body Mass Index (BMI) will be calculated and recorded at the visits indicated in [Table 2](#) using the following formula: $Weight (kg) / [height (m)]^2$.

6.3.9 Electrocardiograms

All 12-lead ECGs will be complete, standardized recordings performed at the visits indicated in [Table 2](#). The subject must rest in a supine position before the ECG is obtained. ECG tracings (paper or electronic) will be reviewed and interpreted by a qualified clinician. ECG tracings and results (ventricular rate, PR, RR, QRS, QT, QTcF and QTcB intervals) will be included and summarized in the subject's study records.

6.3.10 Laboratory Evaluations

The laboratory evaluations will include, but are not be limited to, the following:

- Clinical chemistry serum tests
 - Sodium (Na), potassium (K), chloride (Cl), phosphorus (P), calcium (Ca), carbon dioxide (CO₂), blood urea nitrogen (BUN), creatinine (CR), uric acid
 - Alanine aminotransferase (ALT/SGPT), aspartate aminotransferase (AST/SGOT), gamma-glutamyl transpeptidase (GGT), alkaline phosphatase (ALP), total bilirubin (TBIL), lactate dehydrogenase (LDH), thyroid stimulating hormone (TSH). (The TSH will only be done at Screening; if the TSH level is outside of the laboratory reference range, a reflex free T4 test will automatically be performed by the central lab.)
 - HbA1c (Screening only)
 - Glucose
 - Albumin (ALB), total protein
 - Prolactin
 - Creatine kinase (CK)/creatinine phosphokinase (CPK)

- Lipid panel
 - Total cholesterol, HDL-cholesterol, triglycerides, LDL-cholesterol, Cholesterol/HDL ratio, Non-HDL cholesterol
- Serum pregnancy test for women of child-bearing potential
- Urine pregnancy test for women of child-bearing potential
- Hematology tests
 - Complete blood count (CBC) including:
 - White blood cell (WBC) count
 - Complete differential (relative and absolute)
 - Hematocrit (Hct), hemoglobin, red blood cells (RBC), platelets
 - Reticulocyte count
- Urinalysis
 - Blood, RBCs, WBCs, protein, glucose, ketones, specific gravity, pH
- Urine toxicity screen
 - The following controlled substances will be tested with a urine toxicity screen according to the schedule presented in [Table 3](#): amphetamine, barbiturates, benzodiazepines, cocaine, methadone, morphine/opiates, methamphetamine, marijuana (THC), phencyclidine (PCP), ecstasy (MDMA). Negative drug screens are required for study eligibility.
 - Subjects who test positive and have a valid prescription for a controlled substance may be retested if they agree to abstain from the medication for the length of their participation in the study. The repeat test, and any other tests, must be negative for them to participate in the study.

Laboratory evaluations will be completed according to the schedule presented in Table 3 and procedures detailed in the laboratory Manual of Procedures (MOP). Additional safety testing may be performed at the discretion of the Investigator or designee.

Table 3 Safety Laboratory Evaluations

Visit	Tests
Screening (initial visit)	CHEM, TSH, reflex free T4, CBC, UA, urine toxicity screen, and serum pregnancy test
Baseline (Week 0)	CHEM, CBC, UA, urine toxicity screen, and serum and urine pregnancy tests
Week 5	CHEM, CBC, UA, urine toxicity screen, and serum and urine pregnancy tests
Week 10	CHEM, CBC, UA, and serum and urine pregnancy tests

CBC=complete blood count; CHEM=clinical chemistry serum tests; UA=urinalysis

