1.3.1 Known Potential Risks

The Prescribing Information for NUPLAZID[®] (pimavanserin) tablets for oral use (ACADIA Pharmaceuticals Inc., 2017) indicates the following contraindication and includes the following Boxed Warnings:

- Contraindication: NUPLAZID is contraindicated in patients with a history of hypersensitivity reaction to pimavanserin or any of its components. Reactions have included rash, urticaria, tongue swelling, circumoral edema, and throat tightness.

- **Boxed Warnings:**
 - Increased mortality in elderly patients with dementia-related psychosis; elderly patients with dementia-related psychosis treated with antipsychotic drugs are at an increased risk of death
 - Not approved for the treatment of patients with dementia-related psychosis unrelated to the hallucinations and delusions associated with Parkinson's disease psychosis

The increased mortality in elderly patients is based on information regarding antipsychotic drugs generally, rather than on specific pimavanserin data. Antipsychotic drugs increase the all-cause risk of death in elderly patients with dementia-related psychosis. Analyses of 17 dementia-related psychosis placebo-controlled trials (modal duration of 10 weeks and largely in patients taking atypical antipsychotic drugs) revealed a risk of death in the drug-treated patients of between 1.6- to 1.7-times that in placebo-treated patients. Over the course of a typical 10-week controlled trial, the rate of death in drug-treated patients was about 4.5%, compared to a rate of about 2.6% in placebo-treated patients. Although the causes of death were varied, most of the deaths appeared to be either cardiovascular (e.g., heart failure, sudden death) or infectious (e.g., pneumonia) in nature.

The Warnings and Precautions section of the Prescribing Information for pimavanserin also includes QT interval prolongation. Pimavanserin prolongs the QT interval. The magnitude of effect in humans has been assessed in a thorough QT study with doses of pimavanserin ranging from 17 to 68 mg and in a Phase 3 Parkinson's Disease psychosis program with a clinical dose of 34 mg. An average prolongation of approximately 5-8 ms was observed.

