The use of pimavanserin should be avoided in patients with known QT prolongation or in combination with other drugs known to prolong QT interval including Class 1A antiarrhythmics (e.g., quinidine, procainamide) or Class 3 antiarrhythmics (e.g., amiodarone, sotalol), certain antipsychotic medications (e.g., ziprasidone, chlorpromazine, thioridazine), and certain antibiotics (e.g., gatifloxacin, moxifloxacin). Pimavanserin should also be avoided in patients with a history of cardiac arrhythmias, as well as other circumstances that may increase the risk of the occurrence of torsade de pointes and/or sudden death, including symptomatic bradycardia, hypokalemia or hypomagnesemia, and the presence of congenital prolongation of the QT interval.

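### The protocol names low magnesium as a reason to avoid pimavanserin, but its listed Screening chemistry panel measures potassium and not magnesium

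*Protocol*

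**What the plan says.** Protocol 1.3.1 (Known Potential Risks) reports that pimavanserin prolongs the QT interval: "An average prolongation of approximately 5-8 ms was observed" across a thorough QT study at 17 to 68 mg and a Phase 3 program at 34 mg. It then says the drug should be avoided in several circumstances that raise the risk of torsade de pointes or sudden death, "including symptomatic bradycardia, hypokalemia or hypomagnesemia, and the presence of congenital prolongation of the QT interval".

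Protocol 6.3.10 sets the laboratory tests. The Screening row of Table 3 is "CHEM, TSH, reflex free T4, CBC, UA, urine toxicity screen, and serum pregnancy test", and the footnote gives "CHEM=clinical chemistry serum tests". The list of those tests opens with "Sodium (Na), potassium (K), chloride (Cl), phosphorus (P), calcium (Ca" and continues through carbon dioxide, renal and liver tests, glucose, proteins, prolactin, creatine kinase and lipids. Magnesium is not in it. SAP 14.2 gives the same chemistry list without TSH, again without magnesium. SAP Table 4 has alert limits for potassium and no magnesium row.

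The 6.3.10 list is introduced as non-exhaustive. The section also refers to "procedures detailed in the laboratory Manual of Procedures (MOP"), a document not supplied, and adds: "Additional safety testing may be performed at the discretion of the Investigator or designee".

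**The concern.** The protocol pairs two electrolyte disturbances as reasons not to give the drug, then lists a test for only one. Low magnesium is found directly by a blood test. If that test is not run, a subject with an unrecognized deficiency can be dosed with a QT-prolonging drug in the circumstance that Section 1.3.1 advises against.

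What is at stake is subject safety alone. A pre-dose ECG shows QT prolongation that already exists. It does not show a correctable factor that could make a further 5 to 8 ms more hazardous. Detection before the first dose matters more because exposure does not end quickly: Protocol 1.1.1 gives mean half-lives of about 57 hours for pimavanserin and 200 hours for its active metabolite.

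**Working it through.** No power, alpha or sample-size figure is in dispute. The check sets the sections side by side and makes three small counts.

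**1. Each circumstance in the 1.3.1 warning against its listed check**

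| Circumstance in 1.3.1 | Listed check |
|---|---|
| Known or congenital QT prolongation | Exclusions 17 and 18 |
| QT-prolonging drugs | Appendix A |
| History of arrhythmia | Exclusion 24; medical history (6.3.5) |
| Symptomatic bradycardia | Pulse (6.3.7); ECG ventricular rate (6.3.9) |
| Hypokalemia | Potassium in the chemistry panel (6.3.10) |
| Hypomagnesemia | No listed measurement |

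**2. Count of results named in 6.3.10 (serum chemistry and lipids)**

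- Electrolytes and renal (Na, K, Cl, P, Ca, CO2, BUN, creatinine, uric acid): 9
- ALT, AST, GGT, ALP, bilirubin, LDH, TSH: 7
- HbA1c: 1
- Glucose: 1
- Albumin, total protein: 2
- Prolactin: 1
- Creatine kinase: 1
- Lipid panel: 6

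Total: 9 + 7 + 1 + 1 + 2 + 1 + 1 + 6 = 28, of which magnesium is 0. SAP 14.2 drops TSH, giving 28 − 1 = 27, and magnesium is again 0.

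**3. Subjects planned to receive pimavanserin (Protocol 9.5)**

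47 from Stage 1 + 49 first exposed in Stage 2 = 96.

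**4. Age of a Screening value at the first pimavanserin dose**

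- Stage 1: 8 to 21 days (Protocol 6.5.1.1).
- Stage 2: the Week 5 target is Study Day 36 (SAP Table 2), which is 35 days after first dosing. That gives 8 + 35 = 43 days to 21 + 35 = 56 days, before the ±3-day visit window.

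**5. Whether another provision would find unrecognized low magnesium**

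- The open list, the laboratory manual and investigator discretion permit a magnesium test. Nothing in the protocol or SAP requires one.
- Protocol 6.3.5 says "A complete medical and psychiatric history will be obtained from each potential subject". That can reveal a known deficiency, which exclusions 1, 2, 4 or 5 could act on. It does not reveal an unknown one.
- Exclusion 4 acts on laboratory abnormalities that have been found, so a test that was not run cannot trigger it.
- The QTcF limits, the drug restrictions in Appendices A and B, and ECGs at Screening, Baseline and Weeks 1, 5, 6 and 10 limit QT risk but do not measure magnesium. The first scheduled ECG on drug is at Week 1, or Week 6 for those switched at Week 5.

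**The case against.** The strongest objections, and what stands of each:

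- **The warning is background, not a study rule.** It sits in the risk section and follows the drug's labelling. No eligibility criterion sets a magnesium or potassium limit, so no instruction is broken. This is correct. The point is that the plan does not act on its own warning, not that it contradicts an eligibility rule.
- **The laboratory manual may already include magnesium.** This also stands. Only the absence of a listed routine test is shown; whether magnesium was measured cannot be determined. If the manual covers it, the fix is one clarifying line.
- **The population is already screened for stability and cardiac risk.** Inclusion 10 and exclusions 3, 8, 11 and 24 narrow the group at risk. They reduce the concern without detecting low magnesium.
- **Potassium has no eligibility threshold either.** True: exclusion 4 rests on investigator opinion, and SAP Table 4 flags post-baseline values for reporting. Even so, a measured value can be judged and an unmeasured one cannot.
- **The fix serves Stage 2 starters less well.** They are 49 of 96, or 51%, and their Screening value would be 43 to 56 days old. This limits the benefit but does not remove it, and those starting in Stage 1 are not affected by it.
- **The benefit is unquantified.** The documents give no prevalence and no event risk. That argues for a modest rating, not for leaving the test out when the blood is already being drawn.

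**Conclusion.** The concern holds as stated. Hypomagnesemia is named beside hypokalemia as a reason to avoid the drug. The listed Screening panel covers potassium and 27 other results, but not magnesium. Of the two named electrolyte disturbances, one has a listed test and one does not, in a trial planning to expose about 96 subjects.

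The conclusion rests on the protocol and SAP lists alone and assumes that neither the laboratory manual nor an investigator adds the test. No number of affected subjects and no QT event risk can be given. This is a worthwhile, inexpensive safety improvement. It has no bearing on alpha, power, the primary analysis or the randomized QTc comparisons.

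**What to change.** Add serum magnesium to the chemistry panel in Protocol 6.3.10 at the Screening draw, with a matching line in SAP 14.2. Review the result before randomization under exclusion 4, at the laboratory check already described in Protocol 6.5.2. The 8 to 21 days between Screening and Baseline leave time for the result. Subjects whose deficiency is corrected could rescreen with the Medical Monitor's permission, as SAP 6 already allows for temporary conditions. If the laboratory manual already includes magnesium, the protocol should simply say so.

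Optionally, repeat the test at the later chemistry draws and add a row to SAP Table 4. A Week 5 sample could not gate the first Stage 2 dose, because drug is dispensed at that same visit.

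The cost is one more analyte (28 + 1 = 29 named results) on blood already drawn: at least 188 assays, plus those for screen failures. A few more screen failures are possible. Their number cannot be derived from the documents, and rescreening would recover some. No new visit, procedure or staff is needed.

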6.3.11 Adverse Event Reporting

Adverse event reporting is described in [Section 7](#).

6.4 Pharmacokinetic Assessments

At Screening, blood samples will be collected for the measurement of the subject's SSRI/SNRI antidepressant plasma concentrations. The results will be provided to the investigator to assess the subject's eligibility for the study.

At Baseline (pre-dose) and at Weeks 1, 3, 5, 6, 8, and 10 blood samples will be collected for the measurement of plasma concentrations of pimavanserin, the metabolite AC-279, and the concomitant SSRI/SNRI antidepressant. These data will remain blinded until the clinical database is unlocked at the end of the study.

The dates and times of the administration of the last 3 doses of study drug, and the concomitant SSRI/SNRI antidepressant, as well as the date and time the blood sample was drawn, will be recorded in source documents and the eCRF at each of the above study visits.

When possible, PK samples for pimavanserin, AC-279, and the concomitant SSRI/SNRI antidepressant should also be collected from subjects experiencing a serious adverse event (SAE) or AE leading to discontinuation. The dates and times of administration of the last 3 doses of both study drug and the concomitant SSRI/SNRI antidepressant prior to the SAE or AE leading to discontinuation, as well as date and time the blood sample was drawn, should also be recorded in source documents and in the eCRF. These data will remain blinded until the clinical database is unlocked at the end of the study.

Additional information for specimen preparation, handling, storage, and shipping can be found in the laboratory MOP.

6.5 Study Schedule

A schedule of the required study procedures and evaluations are outlined in [Table 2](#). Every effort should be made to complete the required procedures and evaluations at the designated visits and times.

6.5.1 Screening

6.5.1.1 Screening Visits (Day -21 to Day -8)

Subjects will report to the clinical research unit for eligibility screening within 21 to 8 days prior to the Baseline Visit (Week 0). Before any study specific procedures are conducted, the subject must sign a written ICF.

During this visit, the following study procedures will be performed:

- Signing of informed consent and if applicable, privacy forms
- Evaluation of inclusion and exclusion criteria
- Evaluation of medical and medication history
- Collection of demographic information
- Evaluation of psychiatric history
- MGH ATRQ
- Schedule SAFER remote interview
- SCID-5-CT
- Routine physical examination
- Urine toxicity screen (done by central lab)
- Serum pregnancy (for all female subjects of childbearing potential)
- Height (cm)
- Weight (kg)
- Body mass index (BMI)
- Oral body temperature (°C)
- Blood pressure (seated)
- Clinical laboratory tests
- PK blood draw for concomitant SSRI/SNRI level
- 12-lead ECG (single recording; before blood sampling or at least 30 minutes after blood sampling). May be repeated once in consultation with the medical monitor.

- Columbia Suicide Severity Rating Scale (C-SSRS) for the following time frames:
 - Suicidal Ideation: Lifetime and past 6 months
 - Suicidal Behavior: Lifetime and past 2 years
- HAMD-17
- MADRS
- CGI-S
- Assessment of concomitant medications
- Assessment of AEs

6.5.1.2 SAFER Interview

To ensure that appropriate subjects are entered into the study, a remote interview will be conducted by [REDACTED] raters. The assessments administered will be the SAFER Interview, which will include the MADRS, the CGI-S, and the MGH ATRQ. The interview will be performed remotely by the [REDACTED] rater, and the subject will be contacted at his or her home or other off-site location between the Screening and Baseline visits, during which all the above assessments will be performed. Sites will be notified of the results within 24 hours of the interview.

6.5.2 Baseline (Week 0)

At Baseline, after Screening procedures are completed and reviewed (e.g., acceptable clinical laboratory tests), the subject will be evaluated for continued eligibility and if qualified, may enter the treatment phase and receive the first dose study drug. Subjects will complete the following procedures at Baseline:

- Physical examination
- Vital signs (pre-dose; sitting [at least 3 minutes] BP, pulse, respiratory rate, and temperature)
- Weight
- 12-lead ECG (single recording; before blood sampling or at least 30 minutes after blood sampling). May be repeated once in consultation with the medical monitor.
- Clinical laboratory tests
- Serum and urine pregnancy tests for women of childbearing potential
- Urine toxicity screen (done by central lab)
- PK blood draw (pre-dose) for pimavanserin, AC-279, and concomitant SSRI/SNRI concentrations
- Assessment of concomitant medications

- Assessment of AEs
- Scales listed in [Table 2](#) (MADRS, HAMD-17, CGI-S, SF-12, SDS, DAI-10, MGH-SFI, KSS, BIS-11, SIS, C-SSRS, AIMS, BARS, and SAS).
 - The C-SSRS time frame is since last visit.
- Randomization
- Dispense and administer first dose of study drug
 - Each subject will be assigned study drug according to the randomization schedule. The first dose will be administered at the clinic; study drug kits will then be dispensed to the subject to take home. It is recommended that the subject take the study drug at approximately the same time each day.

6.5.3 Week 1

Subjects will complete the following procedures:

- Vital signs (sitting [at least 3 minutes] BP, pulse, respiratory rate, and temperature)
- Weight
- 12-lead ECG (single recording; before blood sampling or at least 30 minutes after blood sampling)
- PK blood draw for pimavanserin, AC-279, and concomitant SSRI/SNRI levels
- Assessment of concomitant medications
- Assessment of AEs
- Scales listed in [Table 2](#) (HAMD-17, CGI-S and I, SDS, KSS, BIS-11, SIS, C-SSRS, AIMS, BARS, and SAS)
 - The C-SSRS time frame is since last visit
- Study drug accountability
- Dispense study drug

6.5.4 Week 2

Subjects will complete the following procedures:

- Vital signs (sitting [at least 3 minutes] BP, pulse, respiratory rate, and temperature)
- Weight
- Assessment of concomitant medications
- Assessment of AEs
- Scales listed in [Table 2](#) (HAMD-17, CGI-S and I, SDS, KSS, C-SSRS)

- The C-SSRS time frame is since last visit
- Study drug accountability
- Dispense study drug

6.5.5 Week 3

Subjects will complete the following procedures:

- Vital signs (sitting [at least 3 minutes] BP, pulse, respiratory rate, and temperature)
- Weight
- PK blood draw for pimavanserin, AC-279, and concomitant SSRI/SNRI levels
- Assessment of concomitant medications
- Assessment of AEs
- Scales listed in [Table 2](#) (HAM-D-17, CGI-S and I, SDS, KSS, BIS-11, SIS, C-SSRS)
 - The C-SSRS time frame is since last visit
- Study drug accountability
- Dispense study drug

6.5.6 Week 4

Subjects will complete the following procedures:

- Vital signs (sitting [at least 3 minutes] BP, pulse, respiratory rate, and temperature)
- Weight
- Assessment of concomitant medications
- Assessment of AEs
- Scales listed in [Table 2](#) (HAM-D-17, CGI-S and I, SDS, KSS, C-SSRS)
 - The C-SSRS time frame is since last visit
- Study drug accountability
- Dispense study drug

6.5.7 Week 5

Subjects will complete the following procedures:

- Physical examination
- Vital signs (sitting [at least 3 minutes] BP, pulse, respiratory rate, and temperature)
- Weight

- 12-lead ECG (single recording; before blood sampling or at least 30 minutes after blood sampling)
- Clinical laboratory tests
- Serum and urine pregnancy tests for women of childbearing potential
- Urine toxicity screen (done by central lab)
- PK blood draw for pimavanserin, AC-279, and concomitant SSRI/SNRI levels
- Assessment of concomitant medications
- Assessment of AEs
- Scales listed in [Table 2](#) (HAMD-17, CGI-S and I, SF-12, SDS, DAI-10, MGH-SFI, KSS, BIS-11, SIS, C-SSRS, AIMS, BARS, and SAS)
 - The C-SSRS time frame is since last visit
- Study drug accountability
- Re-randomization (see [Section 9.6.2.2](#))
- Dispense study drug

6.5.8 Week 6

Subjects will complete the following procedures:

- Vital signs (sitting [at least 3 minutes] BP, pulse, respiratory rate, and temperature)
- Weight
- 12-lead ECG (single recording; before blood sampling or at least 30 minutes after blood sampling)
- PK blood draw for pimavanserin, AC-279, and concomitant SSRI/SNRI levels
- Assessment of concomitant medications
- Assessment of AEs
- Scales listed in [Table 2](#) (HAMD-17, CGI-S and I, SDS, KSS, BIS-11, SIS, C-SSRS, AIMS, BARS, and SAS)
 - The C-SSRS time frame is since last visit
- Study drug accountability
- Dispense study drug

6.5.9 Week 7

Subjects will complete the following procedures:

- Vital signs (sitting [at least 3 minutes] BP, pulse, respiratory rate, and temperature)

- Weight
- Assessment of concomitant medications
- Assessment of AEs
- Scales listed in [Table 2](#) (HAMD-17, CGI-S and I, SDS, KSS, C-SSRS)
 - The C-SSRS time frame is since last visit
- Study Drug Accountability
- Dispense study drug

6.5.10 Week 8

Subjects will complete the following procedures:

- Vital signs (sitting [at least 3 minutes] BP, pulse, respiratory rate, and temperature)
- Weight
- PK blood draw for pimavanserin, AC 279, and concomitant SSRI/SNRI levels
- Assessment of concomitant medications
- Assessment of AEs
- Scales listed in [Table 2](#) (HAMD-17, CGI-S and I, SDS, KSS, BIS-11, SIS, C-SSRS)
 - The C-SSRS time frame is since last visit
- Study drug accountability
- Dispense study drug

6.5.11 Week 9

Subjects will complete the following procedures:

- Vital signs (sitting [at least 3 minutes] BP, pulse, respiratory rate, and temperature)
- Weight
- Assessment of concomitant medications
- Assessment of AEs
- Scales listed in [Table 2](#) (HAMD-17, CGI-S and I, SDS, KSS, C-SSRS)
 - The C-SSRS time frame is since last visit
- Study drug accountability
- Dispense study drug

